8.6.1.4 Expected Adverse Events

Investigational Product-Related Risks

In all completed studies of Lymphoseek, involving 553 subjects, only three events (breast pain and injection site pain reported by subjects with breast cancer and injection site irritation reported by a subject with head and neck squamous cell cancer) were deemed definitely related to the administration of Lymphoseek by the investigator. The most common adverse reactions (incident <1%) have been lack of effect (<0.067%), injection site pain (<0.02%) and rash (<0.02%). Adverse events from the radioactive dose are not expected, since the applied radiation doses are far below doses that can cause acute effects in human tissues.

In addition to the Lymphoseek pre-approval clinical studies, post-marketing surveillance shows that Lymphoseek has been administered to more than 180,000 patients with not a single drug-related SAE. Routes of administration included: subcutaneous, intradermal, and peritumoral. The intended route of administration in this study is intravenous.

Precautionary Measures

Special precautionary measures are not considered necessary for this study. In case of emergency, standard emergency procedures will be employed.

Unexpected Adverse Events

An unexpected adverse event is defined as an adverse reaction that in nature and severity is not consistent with the applicable product information (e.g., Investigator's Brochure). Any adverse experience that is not listed in the current Investigator's Brochure or which is, with regard to the specificity or severity, not consistent with the risk information shall be regarded as unexpected.

Examples would be (a) acute renal failure listed in the Investigator's Brochure with a subsequent new report of interstitial nephritis and (b) hepatitis with a first report of fulminant hepatitis. "Unexpected" as used in this definition refers to an adverse drug experience that has not been previously observed and included in the Investigator's Brochure, rather than from the perspective of such experience not being anticipated from the pharmacological properties of the investigational product.

8.6.1.5 Serious Adverse Events

Definition of Serious Adverse Events

Definition

The following SAE definition is based on ICH guidelines and the final rule issued by the Food and Drug Administration (FDA) and effective 06 Apr 1998.

An SAE is classified as any untoward medical occurrence that at any dose:

- results in death, or
- is life threatening, or
- requires inpatient hospitalization or prolongation of existing hospitalization, or
- results in persistent or significant disability/incapacity, or
- is a congenital anomaly/birth defect, or
- is an important medical event (see paragraphs below).

The term ‘life threatening’ in the definition refers to an event in which the subject was at risk of death at the time of the event; it does not refer to an event that hypothetically might have caused death if it were more severe.

Medical and scientific judgment should be exercised in deciding whether it is appropriate to report an AE as serious also in other situations, such as important medical events that may not be immediately life threatening or result in death or hospitalization but may jeopardize the subject or may require intervention to prevent one of the other outcomes listed in the definition above. These should also usually be considered serious. Examples of such events are intensive treatment in an emergency room or at home for allergic bronchospasm or blood dyscrasias or convulsions that do not result in subject hospitalization.

Actions and reporting obligations in case of serious adverse events

The investigator should take appropriate diagnostic and therapeutic measures to minimize the risk to the subject.

If any SAE occurs over the course of the study, investigators or other site personnel will inform Navidea Biopharmaceutical representatives within one day (i.e., within 24 hours) of becoming aware of the SAE. Written notification of the SAE will be emailed to Navidea Biopharmaceuticals Pharmacovigilance at [contact]. For fatal or life-threatening adverse events where important or relevant information is missing, active follow-up is undertaken immediately.

Pregnancy will have the same time reporting obligations to the sponsor as SAEs. Upon notification, Navidea will provide a form for collection of pregnancy information.

All SAEs must also be recorded on the Adverse Event eCRFs.

Notification of the IRB(s)

The sponsor and/or the investigator will notify the IRB(s) about all relevant events (e.g., serious adverse events [SAEs] and Suspected, Unexpected, Serious Adverse Reactions [SUSARs]) according to all applicable regulations.

Notification of the authorities

The sponsor will process and report all relevant events (e.g., SAEs, SUSARs) to the authorities according to all applicable regulations.

Sponsor's notification of the investigators

The sponsor will inform all investigators about reported relevant events (e.g., SAEs, SUSARs) according to all applicable regulations.

8.6.2 Further Safety Assessments

8.6.2.1 Physical Exam

Complete physical examinations will be conducted according to the Schedule of Study Events (see [Appendix 1](#)). Height and body weight will be collected at Visit 1 (Screening). Only body weight will be repeating at the Visit 3 (Follow-Up).

Physical examinations will be performed for the following body systems:

- General Appearance
- Skin/dermatological
- Eyes, ears, nose, throat
- Head and neck (including thyroid)
- Lungs
- Heart
- Abdomen (liver, kidney, spleen, gastrointestinal)
- Lymph nodes
- Musculoskeletal
- Nervous system

8.6.2.2 Vital Signs

Vital signs comprise the measurement of body temperature, heart rate, respiration, systolic and diastolic blood pressure. All measurements will be taken after the subject has been in a resting position for at least 1 minute.

Vital signs will be measured at screening, within 15 minutes before investigational product injection, within 15 minutes post injection, and at the follow-up safety visit.

Any clinically significant change from screening (worsening) that results in a change in subject management will be considered an AE and will be recorded on the AE page of the CRF.

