5.3 Treatment Assignment

In this open-label, non-randomized, multicenter, dose-escalation safety study all subjects will receive IV administration at one of 3 tilmanocept mass doses: 50 µg, 200 µg, or 400 µg. Within each mass dose group, subjects will receive tilmanocept labeled to one of 3 radiolabel Tc 99m doses: 1 mCi, 5 mCi, or 10 mCi.

Group 1 will be the starting dose group. Three subjects will be enrolled into Group 1. If none of the 3 subjects experiences pharmacologic activity or an ADR, 3 subjects will be enrolled in Group 2. However, if one of the first three subjects experiences a pharmacologic activity or an ADR, three more subjects will be treated at the same dose level. If 2 out of 3 or 3 out of 6 subjects experiences a pharmacologic activity or an ADR in Group 1 the MTD cannot be determined. If no additional pharmacologic activity or ADRs are observed in the expanded group, the dose escalation will continue. If one additional pharmacologic activity or ADR is observed, the current dose will be deemed the maximum tolerated dose (MTD). If more than one additional pharmacologic activity or ADR is observed in the expanded group, the previous dose will be deemed the MTD. Dose escalation will continue until the MTD is found or until Group 9 is reached with only one ADR or without any ADRs. If no ADRs are experienced from Groups 1-9, then the MTD will be highest tilmanocept mass dose radiolabeled at the highest level (400 µg/10 mCi).

Group 10 will consist of 6 HC subjects and Group 11 will consist of 6 subjects with active RA. Subjects enrolled in Groups 10 and 11 will be dosed at the dose level that is established as the MTD from Groups 1 through 9. The maximum tolerated dose is defined as the dose below where >33% of subjects experienced an ADR.

NOTE: Adverse Drug Reaction

An Adverse drug reaction (ADR) includes all noxious and unintended responses to a medicinal product related to any dose or dose regimen. The phrase “responses to a medicinal product” means that a casual relationship between a medicinal product and an adverse event is at least a reasonable possibility, i.e. the relationship cannot be ruled out.

In this multi-center trial, doses will be serially assigned in an open label fashion in accordance with [Table 1](#). Investigators who have identified a subject for participation will receive the dose assignment from the sponsor and request that dose from the supporting Cardinal Health pharmacy.

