7.2.2.2 Administration of Tc 99m Tilmanocept

IV administration of Tc 99m tilmanocept will be at study time 00:00. The preferred site of IV placement will be the left or right antecubital vein unless both elbows are primary sites for RA imaging, then the site for IV placement will be between the elbow and the wrist.

The filled syringe(s) will be connected to the Y-port for a slow push injection. At the completion of the injection(s), a 10 cc sterile normal saline flush will be administered.

The IV administration will be performed in the nuclear medicine department by an onsite Certified Nuclear Medicine Technologist or Nuclear Medicine Physician. Subjects will be continuously monitored for adverse events during the Day 1 Baseline Visit.

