7.2.2.3 After Administration of Tc 99m Tilmanocept

Groups 1-9

For subjects enrolled in Groups 1-9, the following procedures will be completed at the specified times:

- Within 15 Minutes (00:01 to 00:15) Post Injection:
 - Assessment of adverse events
 - ECG (completed before vital signs)
 - Vital signs after at least 1 minute in a resting position (body temperature, heart rate, blood pressure, and respiratory rate)

- 60 ± 15 Minutes Post Injection:
 - Assessment of adverse events
 - Whole body planar imaging (anterior/posterior views)
 - Planar image with both hands in the FOV (5 min anterior/posterior views)
 - Additional 3D SPECT or SPECT/CT will be obtained on identified joints of interest.

- 180 ± 15 Minutes Post Injection:
 - Assessment of adverse events
 - Whole body planar imaging (anterior/posterior views)
 - Planar image with both hands in the FOV (5 min anterior/posterior views)
 - Additional 3D SPECT or SPECT/CT will be obtained on identified joints of interest.

Groups 10-11

For subjects enrolled in Groups 10-11, the following procedures will be completed at the specified times:

- Immediately following administration of Tc 99m Tilmanocept (00:00), a PK blood sample will be drawn.
- Within 15 Minutes (00:01 to 00:15) Post Injection:
 - ECG (completed before vital signs)
 - Vital signs after at least 1 minute in a resting position (body temperature, heart rate, blood pressure, and respiratory rate)
 - Assessment of adverse events
- 15 ± 5 Minutes Post Injection:
 - Assessment of adverse events
 - PK blood sampling
 - Whole body planar imaging (anterior/posterior views)

- **60 ± 15 Minutes Post Injection:**
 - Assessment of adverse events
 - PK blood sampling
 - Whole body planar imaging (anterior/posterior views)
 - Planar image with both hands in the FOV (5 min anterior/posterior views)

- **180 ±15 Minutes Post Injection:**
 - Assessment of adverse events
 - PK blood sampling
 - Whole body planar imaging (anterior/posterior views)
 - Planar image with both hands in the FOV (5 min anterior/posterior views)

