8.6.1.2 Categories for Adverse Event Assessment

All AEs will be assessed and documented by the investigator according to the categories detailed below.

Seriousness

For each AE, the seriousness must be determined according to the criteria given in [Section 8.6.1.5](#).

Severity

The severity of an AE is classified according to the following categories, taking into account the possible range of the intensity of the event:

- Mild - The adverse event is transient and easily tolerated by the subject.
- Moderate - The adverse event causes the subject discomfort and interrupts the subject's usual activities
- Severe - The adverse event causes considerable interference with the subject's usual activities and may be incapacitating or life-threatening.

Specific drug treatment

Any specific drug treatment will be documented.

Causal relationship to investigational product

The investigator will use the following definitions to assess the relationship of the adverse event to the use of investigational product:

Definitely related: Event can be fully explained by administration of the investigational product.

Probably related: Event is most likely to be explained by administration of the investigational product rather than the subject's clinical state or other agents/therapies.

Possibly related: Event may be explained by administration of the investigational product or by the subject's clinical state or other agents/therapies.

Probably not related: Event is most likely to be explained by the subject's clinical state or other agents/therapies, rather than the investigational product.

Definitely not related: Event can be fully explained by the subject's clinical state or other agents/therapies.

For causality assessments, events meeting the categories of definitely, probably, or possibly related will be considered to be related to investigational product.

Causal relationship to study procedure

The investigator will use the following definitions to assess the relationship of the adverse event to study procedure:

- Definitely related:** Event can be fully explained by the study procedure.
- Probably related:** Event is most likely to be explained by the study rather than the subject's clinical state or other agents/therapies.
- Possibly related:** Event may be explained by the study procedure or by the subject's clinical state or other agents/therapies.

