9.2 Safety Variables

The primary variable for this study is whether a subject observes any pharmacologic activity or an ADR during their enrollment in the trial. This is a safety endpoint. The pharmacologic activity or ADR must be observed after the dose of Tc99m tilmanocept is administered.

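### Groups 1-9, which set the MTD, have one vital-sign reading after the IV injection on Day 1; repeat it at the 60 and 180 minute time points

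*Combined protocol and SAP*

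**What the plan says.** Section 8.6.2.2 schedules vital signs at screening, shortly before injection, "within 15 minutes post injection, and at the follow-up safety visit". Section 7.2.2.3, the synopsis and the Vital Sign row of Appendix 1 agree. For Groups 1-9 the only post-injection block on Day 1 with vital signs is 00:01 to 00:15. The 60 ± 15 and 180 ± 15 minute blocks list AE assessment and imaging. The next set is at Visit 3, 3 to 7 days after injection (Section 7.2.3).

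Three rules link a reading to the primary endpoint:

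- Section 8.6.2.2: "Any clinically significant change from screening (worsening) that results in a change in subject management will be considered an AE".
- Section 8.6.1.2: "events meeting the categories of definitely, probably, or possibly related will be considered to be related to investigational product".
- Section 5.3: "If none of the 3 subjects experiences pharmacologic activity or an ADR, 3 subjects will be enrolled in Group 2". One affected subject expands the cohort; more can stop escalation.

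Section 9.2 confirms the endpoint: "The primary variable for this study is whether a subject observes any pharmacologic activity or an ADR during their enrollment in the trial".

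Other Day 1 observation is in Section 7.2.2.2: "Subjects will be continuously monitored for adverse events during the Day 1 Baseline Visit". On earlier experience, Section 8.6.1.4 says: "Routes of administration included: subcutaneous, intradermal, and peritumoral. The intended route of administration in this study is intravenous".

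**The concern.** The primary objective is safety and tolerability of escalating IV doses, and Groups 1-9 decide whether the dose goes up. The protocol already has a route from a vital-sign change to an AE, from there to an adverse drug reaction (ADR), and so to the escalation decision. It does not depend on the undefined term pharmacologic activity. It works only if the reading is taken.

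Continuous monitoring and the AE assessments at 60 and 180 minutes pick up what a subject reports or staff can see. They specify no pulse, blood pressure, respiratory rate or temperature. An asymptomatic but clinically significant change between 15 and about 180 minutes would enter the data only if someone chose to measure it.

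The cited human safety record comes from other routes, so it says little about the time course after an IV dose. Section 9.5.4 also promises vital-sign summaries at each time point by dose group; after injection on Day 1 there is one such time point.

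**Working it through.** **Schedule, Groups 1-9** (Sections 7.2.2.3, 7.2.3 and 8.6.2.2, Appendix 1)

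| Time after injection | AE assessment | Vital signs |
|---|---|---|
| 00:01 to 00:15 | yes | yes |
| 60 ± 15 min | yes | no |
| 180 ± 15 min | yes | no |
| 3 to 7 days (Visit 3) | yes | yes |

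**Intervals, counted from minute 15**

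- Now, to the second scan: 165 − 15 = 150 to 195 − 15 = 180 minutes.
- With two added sets: 45 − 15 = 30 to 75 − 15 = 60 minutes, then 165 − 75 = 90 to 195 − 45 = 150 minutes.
- Not addressed: from the 180-minute point to Visit 3, 72 − 3.25 = 68.75 hours to 168 − 2.75 = 165.25 hours.

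**Added sets.** At the maximum of 36 subjects (Section 8.1.1), 2 × 36 = 72. At the planned average of 26.3 (Table 4), 2 × 26.3 = 52.6.

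**Reproducing Table 4 first.** With event probability p per subject, Section 5.3 gives

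P(escalate) = (1 − p)³ + 3p(1 − p)² × (1 − p)³.

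The current dose is the MTD with probability [3p(1 − p)²]²; in all other cases the previous dose is, taking two or more events among the first three as pointing to the previous dose. With Table 4's probabilities (.01, .02, .05, .08, .10, .13, .16, .19, .22), the chance that each of Groups 1 to 9 is the MTD is .002, .012, .039, .071, .103, .136, .153, .148, .065. Table 4 has .152 for Group 7 and the same values elsewhere, so every entry agrees to within .001. The product of P(escalate) over the nine groups, the chance of clearing Group 9, is 0.270. Table 4's MTD row sums to 0.728, which leaves room for that outcome. The average sample size comes to 26.5, against 26.3 stated.

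**Chance findings from the added readings.** The documents give no rate, so let q be an assumed rate per reading, independent across readings. A 3-subject cohort adds 6 readings; nine such cohorts (27 subjects) add 54.

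- At least one finding in a cohort: 1 − (1 − q)⁶.
- At least one in nine cohorts: 1 − (1 − q)⁵⁴.
- Effect on the rule: replace p by p′ = 1 − (1 − p)(1 − q)² in P(escalate) and multiply over Groups 1 to 9. Every chance finding is counted as an ADR, which is the worst case.

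| q per reading | ≥1 in a cohort | ≥1 in nine cohorts | Rule stops escalation, no true events | Clears Group 9, Table 4 probabilities |
|---|---|---|---|---|
| 0 | 0 | 0 | 0 | 27.0% |
| 0.1% | 0.6% | 5.3% | 0.04% | 26.3% |
| 0.5% | 3.0% | 23.7% | 1.0% | 23.4% |
| 1% | 5.9% | 41.9% | 4.0% | 20.1% |
| 2% | 11.4% | 66.4% | 14.4% | 14.4% |

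The two values of 14.4% in the last row are separate results that happen to coincide. Worked entry, q = 1% and p = 0: p′ = 1 − 0.99² = 0.0199, P(escalate) = 0.99547, and 1 − 0.99547⁹ = 0.040.

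**The case against.** The schedule is the same in all four places, so this is a design choice and not an error. No objective fails because of it.

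Much of the risk is also covered. AEs are monitored continuously on Day 1 and assessed at 60 and 180 minutes. To be missed, a change must be silent, arise after the early reading, be clinically significant, alter management and be at least possibly related. That narrows the gap, but it does not close it: observation is not measurement.

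Section 1.3.2 contains IV animal data. Dogs given 75 to 82 times the 400 µg dose are described as unaffected, and sedation in rats came soon after dosing. The rat respiratory study, however, reports higher minute volume at 0.5 to 1 hour at all three doses. It also found no direct effect on respiration rate, and the vital-sign set does not measure volume. This makes a look after 15 minutes reasonable; it predicts no human harm.

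The only modelled effect is a cost, and the benefit has no number. That is fair, and it is why the point is no more than advisable. The low chance-finding rate is also an assumption.

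Other objections limit the scope without removing the point:

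- Section 8.6.2.2 compares with screening, up to 44 days before dosing, and the added readings inherit that comparator.
- Groups 10-11 also lack vital signs at 60 and 180 minutes. They do not set the MTD, and their next set is at 18-20 hours.
- Recording the assessment before the next cohort opens looks like a new step, but Section 5.3 already requires the cohort's ADR status to be known.
- The early reading may be taken at 00:01, so the gap could reach 195 − 1 = 194 minutes and the first split 75 − 1 = 74. The intervals above start at minute 15.

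**Conclusion.** The point holds. Groups 1-9 have one post-injection vital-sign set on Day 1 where three are easily possible, and 150-180 minutes on site pass without a scheduled reading. A significant silent change in that time has no planned way into an escalation rule that would otherwise count it.

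No bias in the MTD is claimed, and no direction or size of effect on it, because the documents give no event rate. Repeat ECGs and the period from about 3 hours to Visit 3 are outside this point. The chance-finding figures rest on assumed, independent rates with every finding counted as an ADR. Requiring a change in management and at least possible relatedness should keep the real rate low; at an assumed 0.1% per reading the cost to escalation is negligible. This is a cheap safety improvement that should be made but is not essential.

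**What to change.** Add the existing vital-sign set at 60 ± 15 and 180 ± 15 minutes, before each scan, in Section 7.2.2.3 (Groups 1-9), Section 8.6.2.2 and Appendix 1. Suggested text for Section 8.6.2.2: *In Groups 1-9 vital signs will also be measured at 60 ± 15 and 180 ± 15 minutes post injection, before imaging.*

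The investigator should judge these readings by the existing AE rule in Section 8.6.2.2, assess relatedness on the Section 8.6.1.2 scale, and record both before the next cohort opens. The escalation rule, AE definition and ECG schedule stay as they are.

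The cost is a few minutes at two time points when staff are already with the subject, two more marks in the Vital Sign row of Appendix 1, the matching CRF fields, and the chance findings quantified above. No new visit, staff or type of procedure is needed.
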